6.3. Clinical Laboratory Results

Laboratory test results (including hematology, coagulation, serum chemistry, and urinalysis) and abnormal laboratory values will be presented in data listings.

CTCAE Version 5.0 laboratory grades will also be presented. CTCAE grades will be derived based on laboratory results and will not factor in clinical evaluations.

Shift tables summarizing the changes from baseline in severity of laboratory grades will be provided for laboratory parameters graded according to CTCAE Version 5.0. Grade 3 or higher laboratory values will be summarized based on the worst grade observed during MIRV treatment or within 30 days of last dose.

Clinically significant values in liver function tests (LFTs) will be summarized by the following categories, using the maximum value while on MIRV. The denominator for the summaries will be the number of patients who had at least 1 non-missing value during treatment. The categories for each test are not mutually exclusive:

- Aspartate aminotransferase (AST)
 - $> 3 \times ULN$
 - $> 5 \times ULN$
 - $> 10 \times ULN$
 - $> 20 \times ULN$

- Alanine Aminotransferase (ALT)
 - $> 3 \times ULN$
 - $> 5 \times ULN$
 - $> 10 \times ULN$
 - $> 20 \times ULN$
- AST or ALT
 - $> 3 \times ULN$
 - $> 5 \times ULN$
 - $> 10 \times ULN$
 - $> 20 \times ULN$
- Total bilirubin (TBILI)
 - >ULN
 - $> 2 \times ULN$
- Alkaline phosphatase (ALP)
 - > 1.5 × ULN
- (AST or ALT) and TBILI (concurrent)
 - AST or ALT > $3 \times$ ULN and TBILI > $1.5 \times$ ULN
 - AST or ALT > $3 \times$ ULN and TBILI > $2 \times$ ULN
- (AST or ALT) and ALP and TBILI (concurrent)
 - AST or ALT > 3 × ULN and ALP < 2 × ULN and TBILI > 2 × ULN

Here, concurrent means that all the associated LFTs must be from the same visit. In addition, worst postbaseline grade for LFTs will be summarized. Because baseline values of LFTs are already taken into account in CTCAE V5.0, shift table from baseline to worst postbaseline grade will not be generated for LFTs.

Results from pregnancy tests will be provided in listings.

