 - a. Systemic antineoplastic therapy within 5 half-lives or 4 weeks (whichever is shorter) prior to first dose of MIRV
 - b. Focal radiation completed at least 2 weeks prior to first dose of MIRV
11. Patients must have stabilized or recovered (Grade 1 or baseline) from all prior therapy-related toxicities (except alopecia)
12. Patients must have completed any major surgery at least 4 weeks prior to first dose of MIRV and have recovered or stabilized from the side effects of prior surgery
13. Patients must have adequate hematologic, liver and kidney functions defined as:

- a. Absolute neutrophil count (ANC) $\geq 1.5 \times 10^9/L$ (1,500/ μ L) without G-CSF in the prior 10 days or long-acting WBC growth factors in the prior 20 days
 - b. Platelet count $\geq 100 \times 10^9/L$ (100,000/ μ L) without platelet transfusion in the prior 10 days
 - c. Hemoglobin ≥ 9.0 g/dL without packed red blood cell (PRBC) transfusion in the prior 21 days
 - d. Serum creatinine ≤ 1.5 x upper limit of normal (ULN)
 - e. Aspartate aminotransferase (AST) and alanine aminotransferase (ALT) ≤ 3.0 x ULN
 - f. Serum bilirubin ≤ 1.5 x ULN (patients with documented diagnosis of Gilbert syndrome are eligible if total bilirubin < 3.0 x ULN)
 - g. Serum albumin ≥ 2 g/dL
14. Patients or their legally authorized representative must be willing and able to sign the informed consent form (ICF) and to adhere to the protocol requirements
 15. Women of childbearing potential (WCBP) must agree to use highly effective contraceptive method(s) (as defined in [Section 5.8.6](#)) while on MIRV and for at least 3 months after the last dose
 16. WCBP must have a negative pregnancy test within the 4 days prior to the first dose of MIRV

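### SAP 6.3 counts liver-test values on MIRV with no baseline comparison, so a patient whose bilirubin or ALP never changes can be tabulated as having a clinically significant value

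*SAP*

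**What the plan says.** SAP 6.3 (Clinical Laboratory Results) sets up the liver table in these words: "Clinically significant values in liver function tests (LFTs) will be summarized by the following categories, using the maximum value while on MIRV". On who is included, it says: "The denominator for the summaries will be the number of patients who had at least 1 non-missing value during treatment". The denominator is not restricted to patients who were below the cut-off at baseline, and there is no baseline column. The rows are AST, ALT, and AST or ALT, each at > 3, > 5, > 10 and > 20 x ULN; TBILI at > 1 and > 2 x ULN; ALP at > 1.5 x ULN; and three rows that combine tests at the same visit.

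The same section plans a summary of the worst post-baseline CTCAE grade for these tests, then says of the liver tests: "Because baseline values of LFTs are already taken into account in CTCAE V5.0, shift table from baseline to worst postbaseline grade will not be generated".

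Protocol 3.1.1, criterion 13, sets the entry limits: "Aspartate aminotransferase (AST) and alanine aminotransferase (ALT) ≤ 3.0 x ULN" and "Serum bilirubin ≤ 1.5 x ULN (patients with documented diagnosis of Gilbert syndrome are eligible if total bilirubin < 3.0 x ULN"). Criterion 13 has seven parts, a to g, and none mentions alkaline phosphatase.

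Protocol 10.3 says that changes and shifts from baseline will be summarised for blood chemistry, with no exception for liver tests. Protocol Table 9 lists ALT, AST, ALP and total bilirubin under serum chemistry.

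**The concern.** The table labels its entries clinically significant and ties them to time on MIRV, so it will be read as a picture of liver abnormality on the drug. Some of its cut-offs lie within what a patient may bring to the trial. For those rows an elevation that was present at screening and never moved is counted in the same way as one that appeared on treatment.

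The study has one arm, so there is no control group to show the background rate. Each patient's own baseline is the only reference inside the trial. The question matters because Protocol 1.5.4 names hepatic abnormalities as a potential risk. Protocol Table 3 also asks for imaging when a Grade 3 hepatic toxicity persists, to see whether it reflects disease progression. The protocol thus accepts that liver tests may be raised for reasons other than the drug.

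**Working it through.** The plan states no figure on this point, so there is nothing to reproduce. The check has two parts: a comparison of rows with entry limits, which uses the documents alone, and an illustration, which rests on assumptions.

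**1. Each row of SAP 6.3 against the entry limits**

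| Rows | Cut-off (x ULN) | Entry limit (x ULN) | Met by an unchanged eligible value? |
|---|---|---|---|
| TBILI (1 row) | > 1 | ≤ 1.5; < 3.0 in Gilbert syndrome | Yes |
| ALP (1 row) | > 1.5 | none | Yes |
| TBILI (1 row) | > 2 | ≤ 1.5; < 3.0 in Gilbert syndrome | Only in Gilbert syndrome |
| AST, ALT, AST or ALT (3 rows) | > 3 | ≤ 3.0 | No; some rise is needed |
| Combined rows (3 rows) | AST or ALT > 3, with TBILI > 1.5 or > 2 | as above | No; the transaminase part needs a rise |
| AST, ALT, AST or ALT (9 rows) | > 5, > 10, > 20 | ≤ 3.0 | No |

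The total is 1 + 1 + 1 + 3 + 3 + 9 = 18 rows. An unchanged eligible value can meet 3 of them, one of these only in Gilbert syndrome. In the two combined rows with TBILI > 2, a patient with Gilbert syndrome may already meet the bilirubin part at entry, but not the transaminase part.

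**2. Illustration with no drug effect**

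Assumptions, none of them in the documents: a stable true level b, log-normal variation within the patient with CV 10% to 30%, and k = 4 to 12 independent on-treatment draws. For cut-off c:

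- s = √ln(1 + CV²)
- p = 1 − Φ(ln(c/b)/s), the chance that one draw exceeds c
- P(maximum > c) = 1 − (1 − p)^k

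Worked case: b = 2.5, c = 3, CV 20%, k = 4. Then s = 0.198, ln(3/2.5)/s = 0.92, p = 0.179, and P = 1 − 0.821⁴ = 0.545.

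| Stable level (x ULN) | Row | P(counted), range over CV and k |
|---|---|---|
| TBILI 1.2 to 1.5 | > 1 | 0.995 to 1.00 |
| ALP 2 | > 1.5 | 0.999 to 1.00 |
| TBILI 2.5 (Gilbert) | > 2 | 0.998 to 1.00 |
| AST 2.5 | > 3 | 0.13 to 0.98 |
| AST 2.0 | > 3 | 0.00 to 0.65 |
| AST 1.0 | > 3 | at most 0.001 |
| AST 3.0 | > 5 | 0.00 to 0.39 |
| AST 3.0 | > 10 | about 0 |

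The first three lines say little more than that a patient who starts above a cut-off will be counted. They do not show how common such patients are. The AST result depends heavily on the assumed CV. At b = 2.5 and CV 15%, s = 0.149 and p = 0.111, which gives about 0.38 for k = 4 and 0.56 for k = 7.

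**3. Possible counts**

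The protocol plans about 110 treated patients. If 2% to 20% of them (assumed) entered above a given bilirubin or ALP cut-off, then 110 × 0.02 = 2.2 to 110 × 0.20 = 22 would be counted in that row with no change on drug.

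**The case against.** The strongest reply is that the liver displays as a whole are not blind to baseline. SAP 6.3 plans a worst post-baseline CTCAE v5.0 grade for these tests and says that this grading takes baseline into account. All laboratory results are listed. Adverse events count as treatment-emergent only if they start on or after first dose or worsen a prior condition. The x ULN table is described as the maximum on MIRV, not as treatment-emergent. It is descriptive and carries no test. This stands as a reason to keep the point modest. It does not repair the table: its rows use no grades, and a listing leaves the reader to do the sorting.

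Three stronger readings are tempting, and the documents do not support them.

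- A reader might infer that the table's cut-offs in general lie at or below the entry limits. Nine of the 18 rows lie clearly above them, and only TBILI > ULN lies below the general limit. For ALP the issue is that no limit exists.
- A reader might infer that an eligible patient can meet the AST/ALT > 3 x ULN rows or the combined rows at entry. The limit is ≤ 3.0 and the rows need > 3, so a further rise is required, though near the limit variation can supply it.
- A reader might infer that the SAP uses its CTCAE reason to excuse the x ULN rows. The sentence is about a shift table of grades and is already worded for grades. The gap is that nothing equivalent is planned for the x ULN rows.

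**Conclusion.** The point holds for three rows: TBILI > ULN, ALP > 1.5 x ULN and, in Gilbert syndrome, TBILI > 2 x ULN. In these the table cannot separate elevation brought into the trial from elevation that arose on MIRV. This follows from setting SAP 6.3 beside Protocol 3.1.1 and needs no assumption. For the AST/ALT > 3 x ULN rows the weakness is limited to patients near the entry limit, and its size depends on an assumed CV. The higher rows are largely unaffected.

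The number of patients involved cannot be derived, because the documents give no distribution of baseline liver tests; the span of about 2 to 22 of 110 only restates the assumed 2% to 20%. The matter is confined to one descriptive safety table and does not touch the analysis of ORR. It merits a change because the remedy is cheap and a single-arm study has no other internal reference. A baseline display would also bring the SAP closer to the shift summaries that Protocol 10.3 promises for blood chemistry.

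**What to change.** In SAP 6.3:

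- For each test, cross-tabulate the baseline x ULN category against the maximum on-treatment category. SAP 3.2 already defines baseline.
- Beside each existing any-value count, including the concurrent rows, add a treatment-emergent count: patients who did not meet the row's cut-off at baseline and meet it on treatment.
- Keep the any-value counts as they are.

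For the concurrent rows the two counts will usually agree, because a value within the entry limits cannot meet the transaminase part. Showing the baseline bilirubin category there identifies patients with Gilbert syndrome who already met the bilirubin part. The change separates pre-existing from new elevation. It does not remove crossings due to variation alone.

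The data are already collected, so the cost is some extra table programming and sparser cells.

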- ^f ECOG, PE, pregnancy test for WCBP, and hematology and chemistry labs (if all parameters are within normal range) do not need to be repeated at C1D1 if performed within the previous 4 days during Screening.
- ^g Vital signs (BP and body temperature) will be measured before start of infusion; post infusion vital signs should be collected as clinically indicated for potential infusion-related reaction.
- ^h Hematology and chemistry labs may be performed up to 4 days prior to D1 of each cycle, and as clinically indicated while on treatment, with results reviewed before each MIRV administration. In the event of severe toxicity, laboratory tests must be repeated as clinically necessary until the toxicity resolves or stabilizes to baseline level.
- ⁱ For women of childbearing potential (WCBP), a urine or serum pregnancy test must be performed within the 4 days prior to D1 of each cycle, and at the 30-Day Follow-up visit. It is recommended to perform monthly pregnancy tests for 3 months after the last dose of MIRV. Additional testing may be performed in accordance with institutional requirements or local regulation.
- ^j Baseline ophthalmic exams will be performed by an ophthalmologist within 14 days before C1D1 and will include the following: visual acuity (with/without corrective lens; whichever best reflects the patient's usual functioning), slit lamp examination, intraocular pressure measurement, and indirect fundoscopy. All patients who have an ophthalmic exam on study treatment (post-baseline) due to emergence of visual signs or symptoms will have a complete ophthalmological examination performed at EOT visit or 30-Day Follow-up visit.
- ^k Ocular symptoms assessment will be performed by the treating physician or other qualified individual before the start of each cycle. For patients reporting > CTCAE Grade 1 ocular symptoms, treatment will be held until the patient is evaluated by an ophthalmologist for a complete examination.
- ^l Radiologic tumor assessment by CT/MRI scan. The same method of radiographic assessment used at Screening must be used at all subsequent radiographic assessments.

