4.1.2. Dose and Schedule for Mirvetuximab Soravtansine

MIRV will be administered at 6 mg/kg on Day 1 of every 3-week cycle (Q3W).

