5.5.1.1. Mirvetuximab Soravtansine-Related Adverse Events

Dose modifications for MIRV-related AEs are described in [Table 3](#).

Table 3: Dose Modifications for Mirvetuximab Soravtansine-Related Adverse Events

Severity Grade (CTCAE v5.0)	Dose Modifications for MIRV ^a
Hematological	
Neutropenia	
Grade 2 and Grade 3	Hold drug until ANC is $\geq 1.5 \times 10^9/L$ (1500 / μ L) and resume at the same dose level
Grade 4	Hold drug until ANC is $\geq 1.5 \times 10^9/L$ (1500 / μ L) and then resume at one lower dose level
Febrile neutropenia Grade 3 or 4 (with a single temperature reading $\geq 38.3^\circ C$ or a sustained temperature of $> 38^\circ C$ for > 1 hour)	Hold drug until ANC is $\geq 1.5 \times 10^9/L$ (1500 / μ L) and then resume at one lower dose level
Thrombocytopenia	
Grade 2 and Grade 3	Hold drug until PLT count is $\geq 100 \times 10^9/L$ (100,000/ μ L) and resume at same dose level
Grade 3 associated with clinically significant bleeding that requires transfusion therapy and Grade 4	Hold drug until PLT count is $\geq 100 \times 10^9/L$ (100,000/ μ L) and then resume at one lower level
Non-hematological	
Nausea and Vomiting	
Grade 3 (despite use of optimal antiemetics)	Hold drug until resolved to \leq Grade 1, then resume at one lower level
Grade 4	Permanently discontinue
Diarrhea	
Grade 3 (despite use of optimal anti-diarrheal treatment)	Hold drug until resolved to \leq Grade 1, then resume at one lower level
Grade 4	Permanently discontinue
Ocular Disorders	Refer to Section 5.5.2
Noninfectious Pneumonitis	Refer to Section 5.5.3
Infusion-related Reactions	Refer to Section 5.5.5

Table 3: Dose Modifications for Mirvetuximab Soravtansine-Related Adverse Events (Continued)

Severity Grade (CTCAE v5.0)	Dose Modifications for MIRV ^a
All Other Non-hematological Toxicities (except AEs related to underlying disease, Grade 3 fatigue, isolated symptomatic Grade 3 biochemistry laboratory abnormalities that last for < 7 days including electrolyte abnormalities that respond to medical intervention)	
Grade 3	Hold drug until resolved to ≤ Grade 1, then resume at one lower level For any Grade 3 hepatic toxicity that does not resolve to baseline within seven days, an abdominal CT scan must be performed to assess whether it is related to disease progression.
≥ Grade 3 Cardiac events (excluding Grade 3 hypertension)	Permanently discontinue
Grade 4 non-hematological toxicities	Permanently discontinue

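### SAP 6.3 counts a combined AST/ALT and bilirubin elevation only when both cut-offs are exceeded at the same visit, so a later bilirubin rise is missed if AST/ALT has already fallen to 3×ULN or below

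*SAP*

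**What the plan says.** SAP 6.3 (Clinical Laboratory Results) introduces all its liver-test categories with one lead-in: they are summarized "using the maximum value while on MIRV". The list holds single-test rows (AST, ALT, AST or ALT, TBILI, ALP) and three combined rows: AST or ALT >3×ULN with TBILI >1.5×ULN; the same with TBILI >2×ULN; and the latter with ALP <2×ULN. For the combined rows it adds: "Here, concurrent means that all the associated LFTs must be from the same visit". No interval is given within which a later bilirubin value may be paired with an earlier transaminase value.

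The same section summarizes Grade 3 or higher laboratory values over treatment plus 30 days after the last dose. It also provides listings of all laboratory results and a worst post-baseline grade summary for liver tests, but drops the baseline-to-worst shift table for them. SAP 3.4 keeps the first non-missing value when a visit has several.

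On sampling, footnote h of Protocol Table 2 says: "Hematology and chemistry labs may be performed up to 4 days prior to D1 of each cycle, and as clinically indicated while on treatment". After severe toxicity, "laboratory tests must be repeated as clinically necessary until the toxicity resolves or stabilizes to baseline level". Dosing is 3-weekly, so scheduled chemistry is 21 days apart on treatment, with further draws at EOT and the 30-Day Follow-up.

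**The concern.** Transaminases and bilirubin need not peak together. If bilirubin crosses its cut-off after AST/ALT has dropped back to 3×ULN or below, a same-visit rule sees two separate single-test abnormalities and no combined one. These rows are the only planned tabulation of joint elevation, because liver injury is not one of the focused safety groups in SAP 6.2 (ocular, peripheral neuropathy, pneumonitis). With about 110 patients, one uncounted patient can turn a reported one into a reported zero.

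Three gaps in the wording add to this:

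- **Maximum.** The lead-in covers the combined rows too, but a same-visit pair cannot in general be built from each test's own maximum. The SAP does not say how the two rules fit together.
- **Unscheduled repeats.** The SAP does not say whether a repeat between cycles is its own visit. If it were assigned to the preceding visit, SAP 3.4 would keep only the first value and could discard the later bilirubin result.
- **Period.** A limit of on-treatment values is narrower than the period used for Grade 3+ values in the same section. Protocol Table 3 provides for holding or stopping MIRV after higher-grade toxicity, so a bilirubin rise after stopping could fall outside the rows.

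**Working it through.** The plan states no figure for this rule, so there is nothing to reproduce. I applied the rule to constructed patients and then sized the gap under assumptions.

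**Step 1. Constructed patients (×ULN, TBILI >2×ULN row)**

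| Patient | First visit | Next visit, 21 days later | Same visit | TBILI 0–30 days after AST/ALT |
|---|---|---|---|---|
| A | ALT 8, TBILI 1.5 | ALT 2.8, TBILI 2.6 | not counted | counted |
| B | ALT 6.0, TBILI 1.2 | ALT 3.4, TBILI 2.6 | counted | counted |
| C | ALT 8, TBILI 1.0 | ALT 4, TBILI 2.6 | counted | counted |

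A fails because 1.5 is not above 2 at the first visit and 2.8 is not above 3 at the second. B and C are sequential too, but are counted because ALT is still above 3 when TBILI crosses. If C were instead judged at each test's maximum, with the maxima required to share a visit, it would fail: the ALT maximum is at the first visit and the TBILI maximum at the second. Two programmers could report different counts for C.

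**Step 2. Fixed durations, 21-day sampling only**

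Assume ALT >3×ULN lasts D days and TBILI >2×ULN lasts B days, starting L days after ALT, with draws every 21 days at a random phase.

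Overlap = min(D, L + B) − L, not below 0. P(same-visit count) = min(1, overlap/21).

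With D = B = 21:

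- L = 0: 21/21 = 100%
- L = 7: 14/21 = 67%
- L = 14: 7/21 = 33%
- L = 21 or 28: 0%

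A 0–30 day window counts 100% at lags 0 to 21 and 67% at lag 28. If ALT stays up for D = 42 days, the same-visit rule counts 100% through lag 21 and 14/21 = 67% at lag 28. The loss therefore depends on how quickly AST/ALT recovers relative to the lag.

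**Step 3. Varying durations, with and without repeats**

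Monte Carlo with assumed inputs: log-normal durations (log SD 0.5), median 14–28 days for ALT >3×ULN and 14–21 days for TBILI >2×ULN; lag uniform over the interval shown; ALT onset uniform within a cycle.

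Share missed = 1 − P(same visit)/P(TBILI draw 0–30 days after an ALT draw).

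| Lag (days) | 21-day draws only | Plus 7-day repeats after first ALT >3×ULN, counted as visits |
|---|---|---|
| 0–7 | about 3–14% | about 0.4–6% |
| 3–14 | about 11–41% | about 4–24% |
| 7–21 | about 26–68% | about 14–50% |

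For example, with medians of 21 and 21 days and lag 3–14 days, scheduled draws alone give 1 − 0.538/0.715 = 25% missed. With weekly repeats this falls to about 9%.

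**The case against.** The strongest reply has four parts.

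First, a reader might infer that every bilirubin rise following a transaminase rise is lost. Patients B and C show otherwise, so that reading fails.

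Second, a reader might infer from the lead-in that both maxima must occur at the same visit. The later sentence defining concurrency is the more specific one and more naturally governs the combined rows. What stands is that the SAP should say so.

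Third, a reader might assume that chemistry is only ever 3-weekly. The protocol allows tests when clinically indicated and requires repeats after severe toxicity. Table 3 also has a rule that begins "For any Grade 3 hepatic toxicity that does not resolve to baseline within seven days", which implies a test between cycles. AST, ALT, ALP and bilirubin are in one panel (Protocol Table 9), so a repeat can supply a same-draw pair. This reduces the gap, as Step 3 shows, but only if repeats count as visits, which the SAP does not settle.

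Fourth, the definition is explicit and labelled, the output is descriptive, and no test depends on it. Single-test rows, worst grades, listings and adverse event tables would still show the abnormal values. That is correct and limits the consequence. None of those outputs, however, pairs the two rises or counts patients who have both.

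**Conclusion.** The concern stands in a limited form. The same-visit rule leaves out patients whose AST/ALT is at or below 3×ULN by the visit at which bilirubin crosses its cut-off, and nothing else in the plan counts them as combined cases. The treatment of the maximum, the mapping of unscheduled repeats and the on-treatment limit are smaller points of wording that affect the same rows.

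The size is uncertain: about 3–68% of sequential cases visible in the draws with 21-day sampling alone, and about 0.4–50% with assumed weekly repeats. These shares rest wholly on assumed durations and lags. They apply only to patients who have such a course, and the documents give no basis for saying how many that would be. They do not show that a case is likely to be lost in this trial. Nor do the documents support a claim that liver injury would be hidden, because the values remain in the single-test rows and listings. This is a cheap improvement, not an error that threatens the trial's conclusions.

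**What to change.** In SAP 6.3:

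1. State that the maximum applies to the single-test rows only.
2. Evaluate the combined rows over all post-baseline samples, scheduled and unscheduled, through 30 days after the last dose, and exempt them from the first-value rule in SAP 3.4. The 30-Day Follow-up may take place up to 30 + 14 = 44 days after the last dose, so say whether its sample is included.
3. Keep the same-visit row. Add a second row counting patients with TBILI above the cut-off on or within a prespecified window after AST/ALT >3×ULN. Thirty days is my suggestion, not a figure from the documents.
4. List every such case with dates, all values and ALP.

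The cost is SAP wording and minor programming, with no new data collection. SAP 1.1 allows changes before final database lock. The downside is that the windowed row may flag a few pairs with another cause, such as tumour obstruction; the dated listing lets these be resolved case by case.
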